4.2.9 Patient reported outcomes (PROs)

The analysis population for HRQoL data will be the subset of the FAS (ITT set).

It should be noted that some centres erroneously collected patient data using the FACT-O at non-protocol visits. These data will not be used in any analyses or summaries, but will be listed in the appendices and flagged accordingly.

The HRQoL benefit of the long PFS delay with olaparib is expected to be observed when placebo patients require chemotherapy earlier as this is when HRQoL may be expected to deteriorate. It is expected that the stability in "HRQoL" over the 24 months following start of randomised treatment will be longer for patients randomised to olaparib than placebo. This will be investigated using the TOI derived from the FACT-O questionnaire.

Change from baseline TOI scores

Change from baseline in TOI score will be regarded as the primary analysis of the FACT-O questionnaire and will be analysed using a mixed model for repeated measures (MMRM) analysis of the change from baseline (defined as prior to first dose) in TOI scores for each visit.

The primary analysis will be to compare the average treatment effect from the point of randomisation for the first 24 months (which will include analysis visits obtained within the first 24 months, i.e. baseline, day 29 (week 4), weeks 12, 24, 36, 48, 60, 72, 84, 96, see Section 3.3.2) unless there is excessive missing data (defined as >75% missing data). If the time to first subsequent chemotherapy when approximately 50% of placebo patients receive chemotherapy does not occur by 24 months post-randomisation then additional time periods will be analysed and will be included on supportive summaries and graphical displays as appropriate.

The MMRM model will include patient, treatment, visit (analysis) and treatment by visit interaction as explanatory variables, the baseline TOI score as a covariate along with the baseline TOI score by visit interaction. Treatment, visit and treatment by visit interaction will be fixed effects in the model; patient will be included as a random effect. Restricted maximum likelihood (REML) estimation will be used. An overall adjusted mean estimate will be derived that will estimate the average treatment effect over visits giving each visit equal weight. For this overall treatment comparison, adjusted mean estimates per treatment group and corresponding 95% CIs will be presented along with an estimate of the treatment difference, 95% CI and p-value. The treatment by visit interaction will remain in the model regardless of significance.

An unstructured covariance matrix will be used to model the within-subject error and the Kenward-Roger approximation will be used to estimate the degrees of freedom. The following provides sample code for implementing the MMRM analysis:

```
proc mixed data=TOI method = reml;
  class TRT VISIT SUBJECT;
  model TOISC = TRT VISIT TRT*VISIT TOIBL TOIBL*VISIT / s ddfm=kr;
  repeated VISIT / type=UN subject=SUBJECT;
  random intercept / subject= SUBJECT;
  lsmeans TRT / at means pdiff diff alpha=0.05 cl;
```

where TRT is the randomised treatment, VISIT is the visit, TOISC is the change from baseline in the TOI score, and TOIBL is the baseline TOI score.

For the estimation of trt*visit means an additional model will be run using all visits and the following Ismeans statement:

lsmeans TRT*VISIT / slice=VISIT pdiff diff alpha=0.05 cl;

If the fit of the unstructured covariance structure fails to converge, the following covariance structures will be tried in order until convergence is reached: toeplitz with heterogeneity, autoregressive with heterogeneity, toeplitz, and autoregressive. If there are still issues with the fit of the model or estimation of the treatment effects, SUBJECT will be treated as a fixed effect.

For each treatment and visit, the adjusted (least squares) mean estimates, corresponding 95% CIs, estimates of the treatment difference, corresponding 95% CIs and p-values will be presented.

During the randomised treatment phase, it is expected that olaparib will not cause harm to HRQoL, this will be demonstrated by comparing the Trial Outcome Index (TOI) best response rates (improved/no change/worsened) whilst on randomised treatment. A contingency table summarising the TOI best change rates will be provided and a CMH analysis including the randomisation stratification factor will be performed.

Date 15 February 2022

An AUC (Area Under the Curve) analysis will also be performed for TOI. For each patient, the AUC will be derived using the trapezoidal rule and including all available scheduled visits. Time-adjusted AUC will be calculated as AUC divided by time from baseline to last HRQoL visit where the patient provides data. The mean time-adjusted AUC will be analysed using analysis of variance (ANOVA) including using the same stratification factor as described for the primary analysis of PFS. Time-adjusted AUC summary statistics (mean, median, minimum, maximum, StD) per treatment arm will be presented. In addition, the analysis table will provide the estimated mean difference between treatment groups, 95% CI and p-value. This analysis will done using the first 24 months of data provided by a patient. For this analysis, for any patient who dies during the first 24 months, data for each question in the FACT-O from the time of death until 24 months will be set to 0. In addition, an analysis using all available data for each patient will be performed.

If deemed appropriate alternative methods may be used (e.g. piecewise linear modelling).

Descriptive statistics and graphs will be reported for the TOI by visits as well as change in these scores from baseline.

Total FACT-O and subscales scores

Descriptive statistics, by visit and change from baseline, will be reported for physical well-being (PWB), functional well-being (FWB) and the ovarian cancer subscale (Additional Concerns) domains. Descriptive statistics will also be provided for the individual questions that make up the additional concerns subscale.

Descriptive statistics, by visit and change from baseline, will also be reported for the emotional well being (EWB) and social well being (SWB) subscales, these two subscales do not form part of the TOI itself.

FACT-O questionnaire compliance (overall compliance and by visit compliance) will be summarised for each treatment group.

For the FACT-O questionnaire compliance table and subsequent tables of descriptive statistics on a visit basis, in addition to individual visits being presented, additional entries will be given for End of treatment and 30 day follow up visits (see section 3.3.3 for description of visit windowing). These visits will not be presented in corresponding figures.

In order to assess the amount of missing data and the reasons for missing data, plots including the number of questionnaires completed/partially completed/missing at each visit will be produced.

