12.2.3.6 Analysis of PRO endpoints

The analysis population for HRQoL data will be the subset of the FAS (ITT) set.

Change from baseline in TOI score will be regarded as the primary analysis of the FACT-O questionnaire and will be analysed using a mixed model for repeated measures (MMRM) analysis of the change from baseline in TOI score for each visit. The primary analysis will be to compare the average treatment effect from the point of randomisation for the first 24 months (which will include visit data obtained at baseline, day 29 (week 4), weeks 12, 24, 36, 48, 60, 72, 84, 96 and the discontinuation and follow-up visits if occurring within the first 24 months) unless there is excessive missing data (defined as >75% missing data). If the time to first subsequent chemotherapy when approximately 50% of placebo patients receive chemotherapy does not occur by 24 months post-randomisation then additional time periods will be analysed and will be included on supportive summaries and graphical displays as appropriate.

The MMRM model will include patient, treatment, visit and treatment by visit interaction as explanatory variables and the baseline TOI score as a covariate. Treatment, visit and treatment by visit interaction will be fixed effects in the model; patient will be included as a random effect. The treatment by visit interaction will remain in the model regardless of significance. Calculation of a suitable adjusted mean estimate will be detailed in the SAP that will estimate the average treatment effect over visits which gives each visit equal weight. The adjusted mean estimates and corresponding 95% confidence intervals will be presented for the overall treatment comparison and by visit for each treatment group.

Date 05 November 2021

Descriptive statistics and graphs will be reported for the TOI by visits as well as change in these scores from baseline. These will also be reported for the physical well being (PWB), social well being (SWB), emotional well being (EWB), functional well being (FWB) and the ovarian cancer subscale (Additional Concerns) domains.

Summary tables of Trial Outcome Index (TOI) best change rates will be provided.

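### The TOI repeated-measures model adds a redundant random patient intercept to an unstructured covariance, which can trigger an unnecessary change of covariance structure

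*SAP*

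**What the plan says.** SAP 4.2.9 makes the change from baseline in TOI the primary analysis of the FACT-O questionnaire, using an MMRM fitted by REML. The treatment effect is averaged over the first 24 months with equal weight per visit. The post-baseline visits are "day 29 (week 4), weeks 12, 24, 36, 48, 60, 72, 84, 96", which is nine.

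The covariance is specified twice. In words, patient is a random effect and "An unstructured covariance matrix will be used to model the within-subject error". In the sample code, one line is "repeated VISIT / type=UN subject=SUBJECT" and another is "random intercept / subject= SUBJECT". For inference, "the Kenward-Roger approximation will be used to estimate the degrees of freedom".

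The SAP then gives a switching rule: "If the fit of the unstructured covariance structure fails to converge, the following covariance structures will be tried in order until convergence is reached". The order is heterogeneous Toeplitz, heterogeneous autoregressive, Toeplitz, autoregressive. If fitting or estimation problems remain after that, patient becomes a fixed effect. Nothing says that the random intercept is dropped in the fallback models.

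Protocol 12.2.3.6 also states that "patient will be included as a random effect", but it names no covariance structure.

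**The concern.** The random intercept and the unstructured matrix describe the same thing, the covariance between visits within a patient. Fitting both leaves one parameter with no information of its own, so the likelihood is flat in one direction and the Hessian is singular.

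That would be a cosmetic matter if nothing depended on convergence. Here the choice of model does. A fit that stops because of the redundant parameter moves the analysis down the fallback list although the data would support the unstructured matrix. The later structures on that list impose patterns on the covariance that may not hold, and the model-based standard errors inherit any error.

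**Working it through.** The SAP states no numerical figure for this model, so there is none to reproduce. The check concerns identifiability and its consequences.

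**1. Parameter count.** With T = 9 visits, an unstructured R has 9 × 10 / 2 = 45 parameters. The random intercept adds one variance s², giving 46. The marginal covariance is V = R + s²J, where J is the 9 × 9 matrix of ones. For a given V, any pair (s², V − s²J) with V − s²J positive definite gives the same V. The admissible range is 0 ≤ s² < 1 / (1′V⁻¹1). For example, with an assumed SD of 13 and a common correlation of 0.6, the limit is 169 × (1 + 8 × 0.6) / 9 = 108.9.

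**2. Rank of the mapping from parameters to V, intercept retained.**

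| Structure | Parameters | Rank |
|---|---|---|
| Unstructured | 45 + 1 = 46 | 45 |
| Heterogeneous Toeplitz | 9 + 8 + 1 = 18 | 18 |
| Heterogeneous AR(1) | 9 + 1 + 1 = 11 | 11 |
| Homogeneous Toeplitz | 9 + 1 = 10 | 9 |
| Homogeneous AR(1) | 2 + 1 = 3 | 3 |

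Homogeneous Toeplitz fails for the same reason as unstructured: adding a constant to a Toeplitz matrix leaves a Toeplitz matrix.

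**3. Effect on the estimate.** One data set was simulated with 391 patients (SAP 1.3), split 261 to 130 for the 2:1 allocation, and nine visits. The SDs, correlations and dropout were assumed.
- Unstructured alone: −2 REML 12656.786, treatment difference 2.438, SE 0.847.
- Fixing s² at 0, 10.7, 21.4 and 38.6 (limit 42.9), with R reduced to match, left all three values unchanged.
- Two free fits of unstructured plus intercept, from different starting values, converged to s² = 0.012 and s² = 0.717. Their −2 REML, difference and SE were the same to optimiser precision.
- The smallest scaled eigenvalue of the information matrix was 0.0044 for unstructured alone and 0 with the intercept. With a generalised inverse, Kenward-Roger gave SE 0.8493 and 333.2 df in both cases.

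**4. Size if a fallback is triggered.** The assumptions are complete data, nine visits, SD rising from 9 to 15 and decaying correlation, with each structure fitted as the closest approximation to the assumed covariance.
- Heterogeneous Toeplitz plus intercept (first fallback): SE of the 24-month average 0.2% to 1.0% too large; per-visit SEs within −1.5% to +4%.
- Heterogeneous AR(1) plus intercept (second): SE of the average up to about 5% too small.
- Homogeneous AR(1) (fourth): one variance is imposed on all visits. With SDs equally spaced from 9 to 15, the mean variance is 12² + 3.75 = 147.75, so the common SD is 12.16. Then 12.16 / 9 = 1.35 (+35% at week 4) and 12.16 / 15 = 0.81 (−19% at week 96). With the intercept kept, the SE of the average stays within −0.4% to +1.7%.

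**5. The last fallback.** With patient as a fixed effect, the design has 27 visit-specific columns (9 × 3: visit, treatment by visit, baseline by visit) and 391 patient columns, 418 in all. Its rank is 415, because the overall mean, treatment and baseline TOI are constant within a patient and so are absorbed by the patient columns. Adding the visit-averaged treatment contrast raises the rank to 416. The contrast is therefore outside the row space of the design and cannot be estimated.

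**The case against.** The strongest reply is that the over-parameterisation is harmless. The arbitrary quantity is the split between s² and R, which nobody reports. The total covariance, treatment difference, confidence interval and p-value are those of an ordinary unstructured MMRM. This stands, so a reader who infers that the specified model cannot be fitted goes further than the evidence.

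A reader might also infer that falling back is the expected outcome. The documents do not support that. The SAP's trigger is failure to converge; it does not name a Hessian warning on a converged fit as a trigger. Both trial fits converged, and how the sponsor's software would behave cannot be settled from the text.

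Nor should the standard-error risk be taken from AR structures without a random intercept, for which errors of 14% to 26% in the SE of the average can be calculated. The plan never drops the intercept, so it does not contain those models. The first fallback that it does contain is identified and close to benign.

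Finally, the SAP also plans a time-adjusted AUC analysis and a CMH analysis of TOI, neither of which uses this covariance. FACT-O collection ended with the primary analysis (Protocol 6.5, SAP 3.3.1). These points limit the importance of the problem. They do not justify keeping a parameter that contributes nothing and can only disturb the fit, and they do not rescue the fixed-effect fallback.

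**Conclusion.** The point holds as a defect of specification with a limited consequence. The redundancy is a matter of algebra and needs no assumption about the data: one parameter too many under the unstructured matrix, and one too many under homogeneous Toeplitz. If the fit converges, the reported TOI result is unaffected. If it does not, the covariance structure changes because of a coding redundancy. The likely cost is then about 1% or less in the SE of the 24-month average at the first fallback and up to about 5% at the second. Only the last-ranked AR(1) structure gives large per-visit errors. These sizes rest on the assumed SDs and correlations and on complete data.

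TOI is tested at a two-sided 5% level outside the PFS/PFS2/OS procedure (SAP 4.2.1), so no alpha-controlled claim is touched. The fixed-effect fallback is the one step that fails outright, because it cannot deliver the overall treatment comparison. The protocol sentence is not an error in itself, since no covariance structure is attached to it.

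**What to change.** In SAP 4.2.9:
- Delete the `random` line, and the statement that patient is a random effect, for the unstructured and homogeneous Toeplitz models. Keep the intercept only with heterogeneous Toeplitz and the two autoregressive structures, where it is identified.
- Report the unstructured-only fit as the primary TOI analysis, and let the fallback list apply only if that fit fails to converge. The additional model for treatment-by-visit means needs the same change.
- Remove the fallback with patient as a fixed effect.
- Record the departure from Protocol 12.2.3.6 in SAP Section 6.

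The SAP is dated after the primary PFS analysis, so the report should also state which covariance structure was actually used for TOI and, if it was not unstructured, give the unstructured-only result beside it.

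The cost is one line of code, a few sentences and at most one refit of existing data. Nothing is lost: the unstructured-only model is fully identified (45 parameters, rank 45), and in the check it returned the same estimate and SE. Replacing Kenward-Roger with sandwich standard errors is not needed for this point.

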3.3 Patient Reported Outcome (PRO) Variables

3.3.1 FACT-O

Patient reported health-related quality of life (HRQoL) will be assessed using the Functional Assessment of Cancer Therapy – Ovarian (FACT-O) questionnaire (Basen-Enquist K et al 2001). The FACT-O is composed of the following sub-scales: physical, social/family, emotional, and functional well-being as well as the additional concerns scales consisting of specific ovarian cancer symptoms.

The endpoint for HRQoL analysis will be the Trial Outcome Index (TOI), (Cella D et al 1993) an established single targeted index derived from the FACT-O questionnaire and it is considered to target the most relevant symptoms together with function and physical well-being and can be directly related to signs and symptoms and AEs. The TOI is composed of the following scales of the FACT-O: physical and functional well-being and additional concerns (ovarian cancer subscale).

Data relating to the FACT-O will be self-reported through patient questionnaires according to the study plan. Patients will be asked to report their HRQoL over the course of the previous 7 days. All patients will be asked to complete the FACT-O. The FACT-O questionnaire will be administered at baseline, at Day 29, then in line with the RECIST assessments every 12 weeks (+/- 7 days) for 156 weeks, then every 24 weeks (+/- 7 days) up to the data cut off for the primary analysis. In addition, HRQoL questionnaires will be collected at the discontinuation of study treatment visit and 30 days post last dose. Patients who had RECIST 1.1 disease progression will complete the questionnaires during the 12 weekly survival follow-up visits either in person or over the phone.

The Trial Outcome Index (TOI) score will be derived from the sum of the scores of three of the derived subscale scores; physical well-being (7 items), functional well-being (7 items), and ovarian cancer subscale (11 items) of the FACT-O questionnaire version 4. The total FACT-O score will also be calculated which is made up of the sum of the individual subscale scores: physical well being (PWB), social well being (SWB), emotional well being (EWB), functional well being (FWB) and ovarian cancer subscale (Additional Concerns) (11 items).

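### The last fallback for the TOI repeated-measures model, SUBJECT as a fixed effect, cannot give the treatment differences that SAP 4.2.9 requires

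*SAP*

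**What the plan says.** SAP 4.2.9 makes change from baseline in TOI the primary analysis of the FACT-O. The sample code puts TRT, VISIT, TRT*VISIT, TOIBL and TOIBL*VISIT in the MODEL statement. It uses an unstructured REPEATED covariance and adds "random intercept / subject= SUBJECT".

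Two fits are planned:

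- **24-month model.** The listed visits are "baseline, day 29 (week 4), weeks 12, 24, 36, 48, 60, 72, 84, 96", which is nine after baseline. For the overall comparison the SAP wants arm means and "an estimate of the treatment difference, 95% CI and p-value".
- **All-visits model.** "For the estimation of trt*visit means an additional model will be run using all visits". The required output is: "For each treatment and visit, the adjusted (least squares) mean estimates, corresponding 95% CIs, estimates of the treatment difference", with 95% CIs and p-values. SAP 3.3.1 schedules the FACT-O at Day 29 and then "in line with the RECIST assessments every 12 weeks (+/- 7 days) for 156 weeks, then every 24 weeks".

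If the unstructured covariance does not converge, the SAP tries, in order, "toeplitz with heterogeneity, autoregressive with heterogeneity, toeplitz, and autoregressive". If trouble with the fit or with the treatment estimates remains, the final rule is: "estimation of the treatment effects, SUBJECT will be treated as a fixed effect". No other contrast, coding or estimand is given for that step.

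Protocol 12.2.3.6 has patient as a random effect only. SAP 6 does not list the fixed-SUBJECT step among the changes from protocol.

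**The concern.** This is a parallel-group trial. Each patient has one randomised arm and one baseline TOI, so both are constant across that patient's visits. A separate fixed intercept for every patient uses up all the between-patient information, and that is the only information on the treatment difference. The rule is meant to rescue estimation of the treatment effect, but it removes that effect.

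The TOI comparison serves a named secondary objective and is tested at two-sided 5% (SAP 4.2.1). A fit that reached this step would give neither the required estimate nor its interval and p-value, and the SAP names no replacement for that case.

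**Working it through.** The plan states no figure on this point, so there is none to reproduce. The question is whether the required contrasts are estimable.

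**Inputs.** The fixed effects are those of the sample code in SAP 4.2.9. SAP 1.3 gives 391 randomised patients. The split of 261:130 is assumed from 2:1 allocation; 260:131 gives the same ranks at nine visits. The 24-month model has 9 post-baseline visits. To week 156 there are 14 visits (Day 29 plus weeks 12 to 156, which is 1 + 156/12 = 14). The upper figure of 17 adds weeks 180, 204 and 228 and is an assumption. SAP 5 puts five years after the last randomisation at March 2020, so the last patient entered about March 2015. The latest primary cut-off, 36 months later, is then about March 2018.

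**Algebra.** For patient i in arm a(i) at visit j, with baseline b(i), the mean is

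s(i) + τ[a(i)] + v(j) + (τv)[a(i), j] + β·b(i) + γ(j)·b(i).

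1. Add any constant c to τ for olaparib and subtract c from s(i) for every olaparib patient. All fitted values are unchanged, but the treatment difference at every visit moves by c. So does its equal-weight average over visits, and the data cannot fix either one.
2. The difference at visit j minus the difference at visit k does not move, so between-visit contrasts survive.
3. In the same way, adding c to β and subtracting c·b(i) from s(i) changes nothing, so baseline TOI is aliased too.

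A small fit (20 and 10 patients, 4 visits) shows this. Shifting the treatment coefficient from −0.204 to 4.796 or to −10.204, offset in the patient effects, left the residual sum of squares at 101.664 each time.

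**Rank of the SAP design for V visits.** With SUBJECT out of the fixed effects the rank is 3V. With SUBJECT fixed it is 391 + 3(V − 1).

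| Fit | V | Rank, SUBJECT out | Rank, SUBJECT fixed | Required differences estimable, SUBJECT out | Same, SUBJECT fixed |
|---|---|---|---|---|---|
| 24-month | 9 | 27 | 415 | overall: yes | overall: no |
| All visits | 14 | 42 | 430 | 14 of 14 | 0 of 14 |
| All visits | 17 | 51 | 439 | 17 of 17 | 0 of 17 |

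In each row the 391 SUBJECT columns raise the rank by only 388 (415 − 27, 430 − 42, 439 − 51). The three lost directions are the intercept, treatment and baseline TOI. Between-visit contrasts of the treatment difference stay estimable: 13 of 13 at 14 visits and 16 of 16 at 17. Complete data and one assumed dropout pattern give the same answers.

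**Most favourable coding.** With SUBJECT nested in TRT, the differences are still not estimable while the baseline terms stay in the model. They become estimable only if the arm baseline means are exactly equal or the baseline terms are dropped. The SAP keeps those terms.

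**Code note.** The random intercept is redundant with the unstructured covariance: 45 + 1 = 46 parameters but rank 45 at 9 visits, and 106 with rank 105 at 14. It is also redundant with homogeneous Toeplitz (10 with rank 9, and 15 with rank 14). This does not change the marginal model or the treatment estimate once the fit converges. It does not by itself lead to the last step, because the two heterogeneous structures tried after the unstructured one are identified (18/18 and 11/11 at 9 visits, 28/28 and 16/16 at 14).

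**The case against.** The strongest case against is about reach, because the algebra is not in dispute.

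- **The step is remote.** Five structures come before it, and the last of these, autoregressive plus a random intercept, has only 3 parameters. Nothing in the documents suggests that all five fail. This stands.
- **It cannot mislead.** A non-estimable contrast gives no result rather than a wrong one. SAP 4.2.9 also has CMH and AUC analyses, the latter with difference, CI and p-value, and it allows alternative methods. This limits the damage. But those analyses are different summaries, and the discretionary clause names no replacement for this step.
- **It is late.** The SAP is dated 15 February 2022. The primary analysis is past (SAP 5) and PRO collection has stopped (Protocol 6.5). Changing a pre-specified rule after the analysis it governed is awkward. This is fair, and it makes the record of what was fitted the more useful request.
- **The visit count is uncertain.** SAP 3.3.1 has progressed patients completing forms every 12 weeks, so weeks 168, 192 and 216 are possible and the count could reach 20. The answer is then 0 of 20, so the conclusion does not depend on the range.
- **The code note is conditional.** Heterogeneous Toeplitz with a random intercept loses one rank if all visit variances are exactly equal (17 of 18, 27 of 28). This is true, but it touches only the optional tidy-up.
- **Compound symmetry adds little.** It is a special case of structures already listed, and equal variance and correlation over 14 or more visits is a strong assumption. This is correct as a caution about standard errors. Unlike the present last step, though, it leaves the treatment difference estimable.

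**Conclusion.** The point holds and is minor. Any fit that reaches the fixed-SUBJECT step cannot give the treatment difference, CI and p-value that SAP 4.2.9 asks of it. In the 24-month model the overall difference is lost. In the all-visits model every by-visit difference is lost. These are separate fits, so the two losses need not occur together.

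The result follows from one arm and one baseline value per patient. It does not rest on the assumed allocation split, visit range or dropout pattern. It does assume that TRT, TOIBL and their visit interactions stay in the model, as the SAP has them. PFS, PFS2 and OS are unaffected, because TOI is outside their testing procedure (SAP 4.2.1). The documents do not show whether the step was ever used.

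**What to change.** 1. Delete the fixed-SUBJECT sentence. End the fallback list with a simple identified structure that keeps SUBJECT out of the fixed effects, for example compound symmetry through REPEATED with no RANDOM statement (2 parameters, rank 2 at 9, 14 and 17 visits). The small downside is that model-based standard errors then rest on a simpler covariance assumption.
2. For each of the two fits, state which covariance structure and which SUBJECT specification were used, and confirm that SUBJECT was not fixed.
3. Optional: drop the random intercept from the code when the structure is unstructured or homogeneous Toeplitz.

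The cost is one replaced sentence and a short statement on each fit. No new data are needed, and no re-analysis unless SUBJECT was in fact fixed.
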